- 300 mg GSK3228836 for 12 weeks (loading schedule on Day 4 and Day 11). Participants will continue to receive their stable nucleos(t)ide therapy.

After the 12 weeks of dosing with GSK3228836, there will be a post-treatment follow-up period of 24 weeks.

Brief Summary:

The purpose of this study is to determine the therapeutic mechanism of GSK3228836 in participants with CHB. Study details include:

Study Duration: 37 weeks (45 weeks if include screening and flexible visit windows)

Treatment Duration: 12 weeks

Visit Frequency: Twice a week for the first 2 weeks, once a week through Week 14, once at Week 16, and once every 4 weeks thereafter

Study Hypothesis: GSK3228836 treatment will result in phenotypic changes in intrahepatic immunity associated with loss of HBsAg and treatment-emergent changes in ALT

Health Measurement/Observation: HBsAg <LLOQ

Number of Participants:

The study will enrol approximately 20 participants, but no more than 24.

Note: "Enrolled" means a participant's, or their legally acceptable representative's, agreement to participate in a clinical study following completion of the informed consent and eligibility process. Potential participants who are screened for the purpose of determining eligibility for the study, but do not participate in the study, are not considered enrolled, unless otherwise specified by the protocol.

Intervention Groups and Duration:

[figure not shown]
The total duration of the study, including screening, treatment and post-treatment follow-up, is not expected to exceed 45 weeks.

- 45-day screening window. Eligible participants who fall out of the 45-day window may be re-screened at the discretion of the Investigator/site
- Up to 1 week of pre-treatment assessments (including baseline FNA)
- 12 weeks treatment with GSK3228836
- 24 weeks post treatment follow-up (+ up to 10 days)

There are no plans for dose adjustments. Individual dose adjustments for safety are outlined in the monitoring/stopping criteria.

Data Monitoring/ Other Committee: Yes

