Where liver biopsies were once considered routine in the diagnosis and monitoring of liver disease in patients with CHB, they have been mostly replaced by non-invasive tests in recent years, limiting the opportunity to study the liver-resident immune subpopulations in clinical studies. Research papers have recently described the use of fine needle aspirates (FNAs) as a rapid and better-tolerated alternative to conventional core biopsies for sampling intrahepatic immune cells, including T-cells and cells of the innate immune system, such as liver-resident NK cells. This novel technique has been shown to be safe and effective for repeat sampling of the same patient over several weeks/months, permitting longitudinal analysis of immune responses to therapeutic interventions in clinical trials for the first time [Gill, 2019; Tjwa, 2016; Sprengers, 2005].

In study 212602, it is proposed to perform a total of 5 FNAs at preselected timepoints (plus up to 1 optional FNA) during the 45-week study duration (see Section 1.2). The timing of FNAs has been selected to assess intrahepatic immunological changes at different stages of treatment with GSK3228836, and in the follow-up period (Table 6)

Table 6 Timepoints for Fine Needle Aspirates

FNA number	Time point (Study Week)	Description
1	Week -1	Baseline sample
2	Week 3	Early on-treatment. Preceding anticipated marked declines in serum HBsAg level.
3	Week 5	Anticipated start of HBsAg level <LLOQ in responders and start of ALT flare (Based on review of efficacy data in study ISIS 505358-CS3).
4	Week 13	End of treatment
5	Week 36	End of follow-up
6 (Optional)	Any between Week 6 and Week 36	To be determined following discussion between investigator and medical monitor. May be triggered by changes in serum HBsAg levels or ALT.

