8.2.6.1. Time Period and Frequency for Collecting AE and SAE Information

All AEs and SAEs will be collected from the signing of the informed consent form until the final follow-up visit at the time points specified in the SoA (Section [1.3](#)). However, AEs and SAEs that occur prior to the first administration of investigational medicinal product should be recorded only if assessed as related to study participation (e.g., protocol-mandated procedures or invasive tests).

Medical occurrences that begin before the start of study intervention but after obtaining informed consent will be recorded on the Medical History/Current Medical Conditions section of the case report form (CRF) not the AE section.

All SAEs will be recorded and reported to the sponsor or designee immediately and under no circumstance should this exceed 24 hours, as indicated in [Appendix 3](#). The investigator will submit any updated SAE data to the sponsor within 24 hours of it being available.

Investigators are not obligated to actively seek AEs or SAEs after the conclusion of the study participation. However, if the investigator learns of any SAE, including a death, at any time after a participant has been discharged from the study, and he/she considers the event to be reasonably related to the study intervention or study participation, the investigator must promptly notify the sponsor.

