### Overview of Study Design and Key Features

The schema for all countries except Canada is as follows:

An optional 6th FNA may be included between Weeks 6 and 36 following discussion between investigator and medical monitor.

The schema for Canada is as follows:

\*Baseline (BL) up to 45 days after screening  
 \*\*Visit Day 1, Week 1, up to 14 days after Baseline (BL) 'Week -2' FNA  
 ★Primary analysis

Note: The key difference between the two schema, is the following: Canada site has one less scheduled FNA than the other sites.

Design Features	
 
Phase IIa, single arm, multi-centre open label exploratory study of the therapeutic mechanism of GSK3228836 in participants with HBeAg-negative CHB on stable nucleos(t)ide therapy using repeat fine needle aspirations of the liver for intrahepatic immunophenotyping
 
The total duration of the study, including screening, treatment and post-treatment follow-up, is not expected to exceed 45 weeks.
 

------------------------	---

Overview of Study Design and Key Features	
Study intervention	
 
300 mg GSK3228836 for 12 weeks (loading schedule on Day 4 and Day 11). Participants will continue to receive their stable nucleos(t)ide therapy
 

Study intervention Assignment	
 
N/A. This is a single arm study.
 

Interim Analysis	
 
Data will be incorporated into regular safety reviews by an IDMC and may be used to supplement the safety data review for the Phase IIb B-Clear study (approximately every 3 months).
 
There are 2 interims planned for this study, which align with the following timepoints in the Phase IIb B-Clear study: 
 
Interim 1: approximately 30% participants complete Week 12 to assess safety and futility.
 
Interim 2: approximately 50% participants complete Week 24 to assess safety and futility.
 
 
 
Further details found in a separate Interim Analysis Reporting Analysis Plan.
 

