## 4.5. Safety Analyses

The safety analyses will be based on the Safety Analysis Set, unless otherwise specified.

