### 4.5.2. Adverse Events

An adverse event (AE) is considered treatment emergent if the AE onset date is on or after treatment start date. If AE start date is completely missing and the end date is on or after

the treatment start date, the AE will be assumed to be treatment emergent. All AE summaries will be based on treatment emergent events unless otherwise specified.

Adverse events will be coded using the latest version of MedDRA coding dictionary, to give a preferred term and a system organ class. These preferred terms and system organ classes will be used when summarising the data. The severity of AEs and SAEs will be determined by the investigator according to the DAIDS grading system Version 2.1 [[National Institute of Allergy and Infectious Diseases. Division of AIDS, 2017](#)], unless specified otherwise in the protocol.

For AEs by maximum grade summary tables, if a participant reports an AE more than once within an SOC/PT, the AE with the most severe intensity will be included in summaries. Relationship to study treatment, as indicated by the investigator, is classified as “not related” or “related”. Adverse events with a missing relationship to study treatment will be regarded as “related” to study treatment.

The following AE summaries will be presented:

1. AEs overview: summarize the number and percentage of participants with any adverse event, AEs related to study treatment, AEs leading to permanent discontinuation of study treatment, withdrawal from the study, any serious adverse events (SAE), SAEs related to study treatment, fatal SAEs and fatal SAEs related to study treatment.
2. All AEs by system organ class (SOC) and preferred term (PT)
3. All AEs by SOC and PT and maximum grade
4. All drug-related AEs by SOC and PT
5. All drug-related AEs by SOC and PT and maximum grade
6. Serious AEs (SAEs) by SOC and PT
7. AEs leading to withdrawal from the study by SOC and PT
8. AEs leading to permanent discontinuation of investigational product by SOC and PT
9. AEs leading to withdrawal from the study by SOC and PT and maximum grade
10. AEs leading to permanent discontinuation of investigational product by SOC and PT and maximum grade
11. Fatal AEs by SOC and PT
12. AEs by overall frequency
13. Non-serious AEs by SOC and PT
14. Non-serious drug-related AEs by overall frequency
15. Serious fatal and non-fatal AEs by overall frequency

Number of participants with AEs will be summarized if it is not specified otherwise.

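### Adverse events of the baseline liver FNA that start before the first dose enter none of the 15 AE summaries listed in SAP 4.5.2, and Protocol 8.2.6.1 is unclear about where to record them

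*SAP*

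**What the plan says.** **Timing.** The Protocol synopsis allows "Up to 1 week of pre-treatment assessments (including baseline FNA", and the Schedule of Activities (Protocol 1.3, Table 2) puts the first FNA in the Day -7 to Day -1 column. For Canada, the schema in SAP 1.2 places Day 1 "up to 14 days after Baseline (BL) 'Week -2' FNA". In Protocol 4.2, "it is proposed to perform a total of 5 FNAs at preselected timepoints (plus up to 1 optional FNA".

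**Analysis.** SAP 4.5.2 gives the definition: "An adverse event (AE) is considered treatment emergent if the AE onset date is on or after treatment start date". It then sets the default: "All AE summaries will be based on treatment emergent events unless otherwise specified". SAP 4.5 sets the population: "The safety analyses will be based on the Safety Analysis Set, unless otherwise specified". That set contains participants with at least one dose.

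**Collection.** In Protocol 8.2.6.1, AEs and SAEs before the first administration "should be recorded only if assessed as related to study participation (e.g., protocol-mandated procedures or invasive tests". The next paragraph reads: "Medical occurrences that begin before the start of study intervention but after obtaining informed consent will be recorded on the Medical History/Current Medical Conditions section", and it ends by keeping these occurrences out of the AE pages.

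**FNA outputs.** SAP 6.1.1 plans a listing and summary of how many FNAs were planned and completed. No output on FNA complications is described.

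**The concern.** Repeat liver FNA is the defining procedure of this trial, and it is done for mechanistic research. A reader of the study report would expect harm from it to appear in the AE tables. For the baseline FNA, an event with pre-dose onset will not appear there, although Protocol 9.4.5 plans the incidence of all AEs without a treatment-emergent limit. SAP 4.8, which records changes from the protocol analyses, does not mention the restriction.

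The collection text could make the loss permanent. If a site follows the Medical History sentence, a complication caused by the study is filed as a pre-existing condition and can no longer be found in the AE data.

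**Working it through.** **1. Is the baseline FNA always before Day 1?** Yes, as scheduled: Day -7 to Day -1 in general, and up to 14 days before Day 1 in Canada.

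**2. Which complications are lost from the listed summaries?** An event is treatment emergent if its onset date is not earlier than the first dose date. An onset on Day -1 or earlier fails that test. Of the 15 listed summaries, 0 lift the default, so such an event enters 0 of 15. The section on AEs of special interest (SAP 4.5.2.1) does not lift it either, and FNA complications are not one of its four categories.

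**3. Which are still counted?**
- A delayed complication that starts on or after Day 1.
- An event with a wholly missing start date that ends on or after the first dose date (SAP 4.5.2).
- An event whose partial start date is imputed to the first dose date under SAP 6.2.7.

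**4. Who is covered?** Dosed participants only. Protocol 9.4.5 also puts all safety analyses on the Safety Population, so this is not a departure made by the SAP. An enrolled person who had the baseline FNA but was never dosed is outside the SAP 4.5.2 tables.

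**5. The two collection sentences side by side.**

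| Protocol 8.2.6.1 | Scope | Destination |
|---|---|---|
| First paragraph | Pre-dose AEs and SAEs related to study participation, with invasive tests as an example | Recorded as AE or SAE |
| Second paragraph | Medical occurrences between consent and first dose, no exception stated | Medical History, not AE |

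A pre-dose FNA complication fits both rows. The first rule is the more specific, but the text does not say that it takes precedence.

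**6. Size, in procedures.** Protocol Table 6 schedules FNAs at Weeks -1, 3, 5, 13 and 36, which is 5 and agrees with the stated total. The pre-dose share is 1/5 = 20%. The SAP says Canada has one fewer: 5 - 1 = 4, and 1/4 = 25%. With 20 to 24 participants on the general schedule, that is 20 to 24 baseline FNAs out of 20 x 5 = 100 to 24 x 5 = 120 scheduled. Any Canadian participants lower the total. FNAs are also taken only if the investigator deems it appropriate, so the number performed may be smaller.

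**7. Size, in events (illustration only).** The documents give no FNA complication rate. Let p be an assumed chance that one baseline FNA leads to a complication with onset before Day 1, independent between participants. The chance of at least one among n participants is 1 - (1 - p)^n.

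| p (assumed) | n = 20 | n = 24 |
|---|---|---|
| 1% | 18% | 21% |
| 2% | 33% | 38% |
| 5% | 64% | 71% |
| 10% | 88% | 92% |

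The expected number of such events is n x p: 0.2 to 2.0 for n = 20, and 0.24 to 2.4 for n = 24.

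**The case against.** The strongest reply is that the safety objective concerns GSK3228836, and treatment-emergent summaries suit that objective. A rate of FNA complications is not a study objective, and no comparison with the baseline FNA is planned. That stands, and it limits what should be asked for.

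A reader might also infer several stronger points that the documents do not support:

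- **That no AE output of any kind could show these events.** SAP 6.1.1 presents AEs leading to withdrawal by Study Period, in an appendix whose default population is the Enrolled set. The periods are defined in a separate specification, and the treatment-emergent default is not expressly lifted, so this is a possible partial exception.
- **That a person harmed and never dosed vanishes.** If enrolled, that person appears in the disposition summaries with a reason for withdrawal, and subjects excluded from any population are listed. If handled as a screen failure, SAEs belong to the minimum data (Protocol 5.4).
- **That serious harm goes unreported.** Related pre-dose SAEs are collected and sent to the sponsor within 24 hours. The investigator verifies causality against the product or study participation (Protocol 10.3.5), and deaths are listed.
- **That the two collection sentences are flatly opposed.** The first can be read as a specific rule and the second as a general one. AE/SAE review is scheduled in the same Day -7 to Day -1 column as the baseline FNA, which favours that reading. The wording is loose, and nothing shows that sites would misfile.
- **That later FNA complications are lost.** They are tabulated by preferred term and grade. What is missing is a label of relation to the procedure, since relationship is classified only to study treatment.

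None of this puts a recorded, non-serious, pre-dose FNA complication that did not lead to withdrawal into any described summary.

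**Conclusion.** The point holds in limited form. Under the SAP as written, a baseline-FNA complication with known pre-dose onset is in 0 of the 15 summaries in SAP 4.5.2. This follows from the text and rests on no assumed rate. Loss at collection is only possible, and depends on which sentence of Protocol 8.2.6.1 a site follows.

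The gap covers the pre-dose risk period of 1 in 5 scheduled FNAs (1 in 4 in Canada) and affects chiefly non-serious events. How many events that means is unknown: across assumed rates of 1% to 10% per procedure, about 0.2 to 2.4 are expected in 20 to 24 participants. The documents do not support a claim that the trial hides serious procedural harm, or that it was meant to estimate an FNA complication rate. This is a cheap improvement to safety reporting and does not touch the efficacy analyses.

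**What to change.** 1. **Protocol 8.2.6.1, or the CRF guideline if an amendment is no longer practical.** Add an exception to the Medical History sentence: events assessed as related to study procedures are recorded as AEs.
2. **SAP 4.5.2.** Add one listing and a simple count of AEs and SAEs that start before the first dose and are assessed as related to study participation or procedures. Use the Enrolled set and disregard treatment-emergent status.
3. **Optional.** Extend this to later FNAs, or break it down by FNA number, only if the CRF already captures relatedness to the procedure. The documents do not show whether it does.

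The cost is one extra output and a CRF guideline clarification. Medical History entries dated between the baseline FNA and Day 1 can be queried to recover any misfiled events.

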#### **4.5.2.1. Adverse Events of Special Interest**

The following AEs of special interest will be reported:

- ALT increase
- Vascular inflammation and complement activation
- Thrombocytopenia
- Renal injury

An up to date list of specific MedDRA Queries (SMQs), high level terms (HLTs) or individual preferred terms (PTs) used to identify AESIs is periodically updated and stored in a central location. At the time of DBR, the latest version of the terms will be extracted and used to identify AESIs.

All AEs of special interest will be summarized by SOC and PT, and also summarized by SOC, PT and maximum grade. Serious AESIs will be summarized by SOC and PT. All AEs of special interest will be listed.

Separate outputs will be created for each AESI category (ALT increase, vascular inflammation and complement activation, thrombocytopenia and renal injury) to explore the data in more detail if data permits.

Event Characteristics: The characteristics of all event occurrences during the post-baseline period will be summarized, which looks at event characteristics (serious, drug-related, leading to withdrawal, severe or Grade 3-4, fatal), number of events per participant, outcome, maximum grade or intensity and action taken.

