Thrombocytopenia leading to clinically significant bleeding events	
Two types of thrombocytopenia have been described for the 2'-MOE ASOs [Chi, 2017; Crooke, 2017]. One type is a rapid onset, unpredictable thrombocytopenia. The other more common type is characterised by a gradual decline in platelets leading to mild to severe thrombocytopenia and can be asymptomatic or associated with mild to severe bleeding. In monkeys given GSK3228836, there were incidences of both types in a 39-week study.
 
Thrombocytopenia was not reported in the clinical studies with GSK3228836 (ISIS 505358-CS1 and ISIS 505358-CS3)
	
Laboratory Evaluations: platelet count
 
Stopping Criteria: monitoring and stopping criteria are presented in Section 7.1.3

Drug-Induced Kidney Injury	
Glomerulonephritis has been reported with ASOs and is thought to be a result of the proinflammatory effect of ASOs.
 
No adverse events related to renal function were reported in Study ISIS 505358-CS3
	
Laboratory Evaluations: Serum creatinine, eGFR, urinalysis with microscopy and ACR assessed per the SoA tables
 
Stopping Criteria: Monitoring Schedule and Stopping Rules are presented in Section 7.1.4

Injection site reactions	
Injection site reactions have been reported with ASOs and reported in clinical studies with GSK3228836 (ISIS 505358-CS1 and ISIS 505358-CS3).
 
Injection site reactions were the most common study treatment-related AEs reported and were Grade 1 (mild) and Grade 2 (moderate) in severity.
	
Evaluations: Participants are assessed for injection site reactions at all visits during the on-treatment period.
 
In order to minimize the risk of injection site reaction (ISR), injections should be rotated within each anatomical site or site(s) of injection should be changed administration-to-administration. Injection into areas with ongoing injection site reactions should be avoided.

Regarding COVID-19

In addition to the study related risks listed in [Table 5](#), it should be noted that COVID-19 is a risk for everyone. The magnitude of the risk depends on the prevalence in the population, frequency, duration and closeness of contact with other people, use of protective measures, age, ethnicity, sex and co-morbidities including medications.

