8.2.2. Injection Site Reactions

Injection Site Reactions (ISRs) are any experiences which occur at the site of injection of the study treatment. Participants will be monitored closely for the following in relation to ISRs and ISRs should be recorded as AEs:

- Pain or tenderness
- Erythema or redness
- Induration or swelling
- Pruritus

Injection site reactions will be graded according to the criteria provided in the Division of AIDS (DAIDS) grading table (see [Appendix 3](#)).

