8.2.9. Adverse Events of Special Interest

8.2.9.1. ALT Increases

The liver is a site of accumulation of antisense oligonucleotides and this has been exploited in the treatment of liver related diseases.

Outside the setting of disease reactivation or rebound viremia, the aetiology of ALT increase (flares) in CHB patients is currently uncertain. It has been postulated that ALT flares are evidence of reactivation of the immune system in the liver with accompanying clearance of infected hepatocytes, particularly when observed during immunotherapy or spontaneous loss of HBsAg. Therapeutic ALT flares have been shown to correlate with antiviral effect in blood (i.e. declines in HBV DNA, and/or HBsAg).

A monitoring strategy of ALT is presented in Section [7.1.1](#).

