8.2.9.5. Injection Site Reactions

Injection site reactions were the most commonly reported treatment-related adverse event in previous studies with GSK3228836. Injection site reactions included, but were not limited to, pain, erythema and pruritus. Injection site reactions will be assessed at all dosing visits and, if present, should be reported as AEs.

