## 4.8. Changes to Protocol Defined Analyses

Changes from the originally planned statistical analysis specified in the protocol are detailed in [Table 1](#).

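### Injection site reactions are an adverse event of special interest in the protocol but not in the SAP, so no planned output counts participants with any such reaction or describes events per participant and outcome

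*SAP*

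**What the plan says.** Protocol section "8.2.9. Adverse Events of Special Interest" has five subsections: ALT increases (8.2.9.1), vascular inflammation and complement activation (8.2.9.2), thrombocytopenia (8.2.9.3), renal injury (8.2.9.4) and, last, "8.2.9.5. Injection Site Reactions". The last one states: "Injection site reactions were the most commonly reported treatment-related adverse event in previous studies with GSK3228836". The risk table in Protocol 2.3.1 agrees and adds severity: "Injection site reactions were the most common study treatment-related AEs reported and were Grade 1 (mild) and Grade 2 (moderate) in severity". On collection, Protocol 8.2.2 says: "Participants will be monitored closely for the following in relation to ISRs and ISRs should be recorded as AEs". It names four groups of signs (pain or tenderness, erythema or redness, induration or swelling, pruritus) and grades them by the DAIDS table. The Schedule of Activities has a separate injection site reaction row, marked at every dosing visit.

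SAP 4.5.2.1 opens its list with "The following AEs of special interest will be reported" and gives four bullets, which correspond to Protocol 8.2.9.1 to 8.2.9.4. The same section names the categories again: "Separate outputs will be created for each AESI category (ALT increase, vascular inflammation and complement activation, thrombocytopenia and renal injury". These separate outputs are conditional on the data permitting them. The section also plans AESI summaries by system organ class and preferred term and by maximum grade, a table of serious AESIs, a listing, and an event-characteristics summary that includes events per participant, outcome and action taken.

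**The concern.** The two documents disagree on which events are of special interest. The category left out is the one that earlier experience suggests will be reported most often among treatment-related events. That experience came from four weeks of dosing on six days (Protocol 4.3). This trial doses on 14 days, so it describes tolerability of repeated injection over a longer course.

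A reaction that can follow every injection raises two descriptive questions: how many participants had one at all, and how often it recurred and resolved. The SAP assigns the outputs that answer these questions to its AESI categories. A category missing from the list does not get them.

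**Working it through.** There is no figure in the plan to reproduce. The check compares lists and then traces what each planned table would show.

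**Step 1. Categories.**

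| Protocol 8.2.9 | SAP 4.5.2.1, bullet list | SAP 4.5.2.1, separate outputs |
|---|---|---|
| ALT increases | yes | yes |
| Vascular inflammation and complement activation | yes | yes |
| Thrombocytopenia | yes | yes |
| Renal injury | yes | yes |
| Injection site reactions | no | no |

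Five categories against four. The omission occurs twice in the same section, so it is not a bullet lost in text extraction. The safety section of the SAP (4.5) is not redacted.

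**Step 2. Is it covered or explained elsewhere?** No other visible SAP text mentions injection site reactions. Table 1 in SAP 4.8 lists only the time-to-maximum-ALT change. The SAP version history does not mention the omission.

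**Step 3. What will still be reported.** Because the reactions are recorded as adverse events, they enter these tables of SAP 4.5.2:
- all adverse events by system organ class and preferred term, and by maximum grade (items 2 and 3);
- drug-related events, likewise (items 4 and 5);
- serious events (item 6);
- events leading to study withdrawal (items 7 and 9) and to permanent discontinuation of treatment (items 8 and 10);
- events by overall frequency (item 12).

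**Step 4. What these tables cannot show.** By default SAP 4.5.2 counts participants, not events. Let n_k be the number of participants with at least one reaction under preferred term k, and N the number treated. The number with any injection site reaction then satisfies

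max(n_k) ≤ number with any reaction ≤ min(N, Σ n_k).

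The bounds coincide only in special cases, such as all reactions being coded to one term. Otherwise the tables give a range, because a participant with both pain and erythema is counted in two rows. The system organ class row does not help, since it counts any event in that class. How the four groups of signs will be coded is not in the documents, so the number of rows is unknown.

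Repeated reactions under one preferred term count once per participant, and the maximum-grade table keeps only the most severe. Recurrence is therefore not visible. Within the SAP, events per participant and outcome appear only in the AESI event-characteristics summary.

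**Step 5. Dosing occasions.** The Schedule of Activities marks dosing on Days 1, 4, 8, 11, 15, 22, 29, 36, 43 and 50 (ten) and on Days 57, 64, 71 and 78 (four): 10 + 4 = 14. This is the span over which recurrence would go undescribed. It does not measure how much information is lost.

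**The case against.** The strongest reply is that no protocol-specified analysis has been removed. SAP 4.8 says "Changes from the originally planned statistical analysis specified in the protocol are detailed in" its Table 1, and a reader might infer that an analysis was dropped there without being declared. The documents do not support that. Protocol 9.4.5 prescribes no AESI analysis. It asks for incidence and severity of all, treatment-related and withdrawal-related events, and incidence of serious events, all of which the SAP provides. Protocol 8.2.9.5 requires only that reactions be assessed at dosing visits and reported as adverse events. This part of the reply stands: the fault is a contradiction between the two AESI lists, not a breach of SAP 4.8.

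The omission may also be deliberate. The four SAP categories are the ones for which the protocol refers to a monitoring strategy in 7.1.1 to 7.1.4; 8.2.9.5 refers to none. That is plausible, but it is inference, because the SAP does not say so.

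Third, much is reported anyway. Action taken is partly covered by the discontinuation and withdrawal tables, and any serious reaction would appear among the serious events. With about 20 participants, and at most 24, tables by preferred term stay short. The separate category outputs are conditional even for the four listed categories. All of this stands and limits the weight of the point. It does not supply the count of participants with any reaction, the events per participant or the outcome.

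Finally, the SAP identifies AESIs from a centrally stored term list that is not reproduced and could contain injection site terms. But that list supplies terms for categories the SAP names, and this category is not named.

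**Conclusion.** The point holds as a modest gap in tolerability reporting, worth correcting. The SAP names four of the protocol's five AESI categories without explanation. As a result, three descriptions of injection site reactions are not planned: the number of participants affected, events per participant, and outcome. The pooled AESI listing is also lost.

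Two stronger readings should be resisted. A reader might infer that injection site reactions go unreported; they do not, as Step 3 shows. A reader might also infer that a leading safety risk of this trial is being hidden. The statement that these events were the most common concerns previous studies, where they were Grade 1 or 2. One category in five is a count of headings, not of lost information.

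The conclusion rests on the visible SAP text. The Output and Programming Specification, to which the SAP refers for some details, was not available and might add outputs. No estimand, decision rule, stopping rule or primary result depends on this point.

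**What to change.** In SAP 4.5.2.1, add injection site reactions in both places where the categories are named: the bullet list and the sentence on separate outputs. Identify them by a stated list of high level terms and preferred terms. Apply the same AESI summaries, listing and event-characteristics output as for the other four, and make sure the category output has a row for participants with any injection site reaction.

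If the omission was intended, a sentence of justification in the SAP would explain the difference between the documents, but it would not supply the missing counts.

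The cost is a small SAP edit and one more set of standard outputs. The reactions are already assessed at every dosing visit, graded and recorded as adverse events, so no new data are needed.
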